871 between-biopsy-arm comparisons. With 8 new subjects per arm, there is 75% power to detect a
872 significant difference in mineralizing perimeter with a two-tailed 0.05 level overall F-test if the 3
873 differences from baseline are, for example, 10%, 15% and 21%, assuming a within-group standard
874 deviation of 7%. Similar results were obtained for bone formation rate.

875 Finally, based on current experience, the dropout rate of subjects on HPTH therapy for 5 years could be as
876 high as 1 in 3 (33%). To account for that, 36 new eligible subjects will be randomized to the 3 biopsy
877 follow-up time arms, which should result in at least 24 new subjects being evaluable for the primary
878 analyses of the bone biopsy endpoints at years 1, 2 and 4. Up to 10 additional subjects may be screened
879 but not enter the treatment or randomization phase.

880 **10.3 Randomization and Stratification**

881 While there is only one treatment group, subjects will be randomized 1:1.2:1.4 at baseline to the 3 bone
882 biopsy follow-up times of 1, 2, or 4 years, respectively. Heavier weighting is given to the arms with
883 longer follow-up times as these arms are anticipated to have more dropouts. In addition, the
884 randomization will be stratified on 3 factors, gender (Male/Female), menopausal status (pre / post
885 menopausal), and prior participation in this trial (Yes/No). Stratification on gender is indicated because of
886 known gender-based differences in bone formation. Stratification on menopausal status is indicated
887 because of known hormonal changes that may influence bone mineralization. Stratification on prior
888 participation is indicated because the subjects enrolled under the previous version of the protocol will
889 have their pre-conventional therapy biopsy used as their baseline biopsy (new subjects will have their
890 baseline biopsy at the end of conventional therapy) and the effects of conventional therapy on the biopsies
891 is not known with certainty. In order to avoid potential loss of power in the primary analyses if these 3
892 strata are found to be different, 36 new subjects will be enrolled in one stratum and those eligible to
893 continue from among the 10 currently enrolled subjects will be enrolled in the other stratum.

894 Since the target subject sample size is relatively small and there are 3 binary stratification variables, a

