7.4.1 Primary Efficacy Analyses

Separate primary analyses will be performed for each of the eight primary bone structure and bone remodeling biopsy endpoints listed in section 7.2.1. Since the study was terminated early and is thus under-powered, no corrections for multiplicity will be made in the analyses of the 8 primary efficacy endpoints. For each of these primary bone biopsy endpoints, the primary analysis will test for differences with respect to the time of the biopsy (baseline, 1, 2, and 4 year). These endpoints will be analyzed using repeated measures mixed models with the bone biopsy endpoint as the dependent variable, the baseline value of the bone biopsy endpoint and study cohort as covariates, biopsy time (baseline, 1 year, 2 year, and 4 year) as the repeated measure, and subject as the random variable. The repeated measures will include a time-dependent covariate to adjust the baseline biopsy of Cohort 2 for the time delay between the baseline biopsy and the start of hPTH treatment. This covariate will adjust Cohort 2 for any possible further progression of disease occurring between the baseline biopsy measures and the start of hPTH therapy. An indicator variable in the statistical model will set the effects of this time-dependent covariate to zero for Cohort 3 and for the post-baseline biopsies of Cohort 2.

Pairwise contrasts between the bone biopsy times will be performed within the repeated measures analyses to compare the effects of the biopsy times on the bone biopsy endpoints. Because the sample size for 2-year and 4-year biopsies are reduced in size due to withdrawal and the early termination of the study, the 2-, and 4-year biopsies may be combined into one group provided their effects are qualitatively similar (i.e. the estimates of their effects are in the same direction). If the 2- and 4-year biopsies are qualitatively different then the 4-year biopsies may be dropped from the analysis due to its small sample size. The post hoc pairwise comparisons among the

biopsy time-points will be corrected for multiple comparisons using Fisher's protected LSD with Bonferroni corrections when the overall effect of biopsy year is not statistically significant.

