Residual analysis will be used to confirm that model assumptions are reasonable. Log-transformations of the bone biopsy endpoints will be made if indicated by the residual analysis. The repeated measures will be fit using both a compound symmetry and an unstructured covariance structure. The better covariance structure will be selected as the model with the better Schwarz's Bayesian criterion. If the residual analyses of the statistical models indicate a failure to meet the assumptions of the repeated measures statistical models then other methods of statistical analysis including nonparametric analysis may be considered.

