Parameters derived from the back-scattered electron imaging of the bone biopsies include the spectral calcium mean, peak, width, low, and high. These spectral calcium parameters will be analyzed separately using repeated measures mixed models with the spectral calcium parameter as the dependent variable, the baseline value of the biopsy endpoint and study cohort as covariates, biopsy time (baseline, 1 year, 2 year, and 4 year) as the repeated measure, and subject as the random variable. Because there are only a few subjects with the 4 year biopsy, the 2 and 4 year biopsies may be collapsed into one biopsy group for analysis purposes if the 2 and 4 year biopsies appear to have similar effect sizes and variances. If the 2- and 4-year biopsies are qualitatively different then the 4-year biopsy endpoints may be dropped from the analysis due to their small sample sizes. Pairwise contrasts will be performed within the repeated measures analyses to compare the effects of the biopsy times on the bone biopsy endpoints.

Since these spectral calcium parameters are secondary endpoints, these analyses are considered more exploratory and thus no adjustments will be made for performing multiple secondary analyses. However, post hoc pairwise comparisons within each repeated measures analysis will be controlled for multiple comparisons using Fisher's protected LSD followed by Bonferroni correction if the overall effect is not significant.

Results will be summarized in a table. The effects of hPTH treatment on the spectral calcium endpoint will be illustrated in figures of the mean \pm se (or geometric means with 95% confidence limits) over biopsy time.

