7.4.2.4 Repeated measures analyses of the non-biopsy secondary endpoints

The secondary non-biopsy secondary endpoints are listed in section 7.2.2.

Unlike the biopsy endpoints, the secondary non-biopsy secondary endpoints had measurements at baseline and then every 6 months over the 5 years of the study as compared to biopsies at baseline, 1, 2, and 4 years of hPTH treatment. As a complication, subjects were on hPTH therapy for various lengths of time due to study withdrawal and early study termination. Thus, the effects of study month are not the same for each subject with some subjects on hPTH therapy and some

subjects off hPTH therapy for the later study months. Thus, the 6-month time-points will be reduced to the following experimental time-points: baseline visit, 6-month study visit, end of hPTH therapy, and post-hPTH follow-up visit.

The effect of hPTH therapy over the experimental time-points (baseline, 6-month study visit, last hPTH treatment, and post-hPTH follow-up) on each of the non-biopsy endpoint parameters will be analyzed using repeated measures mixed models with the non-biopsy endpoint as the dependent variable, the baseline value of the non-biopsy endpoint, and study cohort as covariates, the experimental time-point as the repeated measure, and subject as the random factor. If dose is found to improve model fits in the bone-biopsy repeated measures analyses (section 7.4.2.1) then the effect of dose will be added as a covariate to these secondary repeated measures. Pairwise post hoc comparisons will be made to test for endpoints differences among the experimental time-points (baseline, 6-month study visit, last hPTH treatment, and post-hPTH follow-up). The significance of these post hoc pairwise comparisons will be corrected for multiple comparisons using Fisher's protected LSD. When the repeated measures overall effects of study time-point are not significant, Bonferroni corrections will be used to adjust the pairwise contrasts for multiplicity.

Residual analysis will be used to confirm that repeated measures model assumptions are reasonable. Log-transformations of the bone biopsy endpoints will be made if indicated by the residual analysis. The repeated measures will be fit using both a compound symmetry and an unstructured covariance structure. The better covariance structure will be selected as the model with the better Schwarz- Bayesian criterion.

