7.4.2.5 Summary of the effects of hPTH weaning on serum calcium, phosphorus, calcitriol, and biomarkers of bone turnover.

The effects of weaning subjects off hPTH will be summarized descriptively by the study PI.

Mixed models repeated measures analysis will test treatment effects on 10 outcome measures: serum calcium, serum phosphorus, 3 bone turnover markers (Osteocalcin, n-Telopeptide, and Alkaline Phosphatase), and 5 DEXA Bone Mass Density (BMD) parameters. The DEXA bone mass density measures included: AP spine BMD, femoral neck BMD, total hip BMD, Forearm BMD, and whole body BMD. Treatment effects will be summarized at three study time-points: Baseline (immediately at start of hPTH treatment), Treatment (immediately prior to Weaning, i.e. end of hPTH treatment), and Follow-up. The repeated measures analyses will be performed using each of these 10 outcome measures as the dependent variables, with random effects for subject,

and repeated fixed effects for 3 study time-points within a subject. These outcome measures will be log-transformed if necessary to normalize the data. Two covariance structures will be tested (compound symmetry and unstructured) and the covariance structure with the smallest Bayesian Information Criterion (BIC) and the best residual distributional properties will be used. Pairwise post hoc contrasts will be made to compare the effects of treatment at the study time-points. These post hoc pairwise contrasts will be corrected for multiple comparisons using Fisher's protected LSD with Bonferroni corrections when the overall effect of time is not significant.

Rho will provide figures with panel columns for the subject and the panel rows for the time course (baseline, during hPTH, through the start of weaning to the post-hPTH follow-up) of oral elemental calcium and calcitriol dosing, plasma calcium, and PTH dose.

7.4.2.6 Summary of hPTH therapy on nephrocalcinosis and nephrolithiasis by ultra sound and CT

The rate of new, stable, and progressing nephrocalcinosis and nephrolithiasis (NC/NL) in study subjects will be summarized.

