9. CHANGES TO THE ANALYSES PLANNED IN THE PROTOCOL

The study was discontinued early, due to pharmacy issues. Upon termination of new enrollment in June of 2015, subjects began to be slowly weaned off of hPTH. Of the 32 planned, newly enrolled subjects, only 19 were actually enrolled and treated and of these, 8 subjects provided their on-treatment biopsy. This early termination provides less power to detect significant differences in endpoints. We will evaluate the possibility of combining the 2- and 4- year biopsy groups to address this issue (see section 7.4.1 for details).

The primary bone biopsy endpoints have changed. The original primary endpoints included: 1) mineralized perimeter; 2) bone formation rate; 3) cortical width; 4) cortical area; 5) osteoid width; 6) osteoid perimeter; and 7) mineral apposition rate. These primary bone biopsy endpoints have been replaced with the eight primary endpoints listed in section 7.2.1. In the analysis of the pilot study of the first 5 patients as well as other relevant pilot studies, we learned that these are the more informative indices.

The primary and secondary analyses will be performed using repeated measures mixed models rather than the paired t-tests, ANOVA, and ANCOVA analyses as stated in the protocol.

Although the protocol specifies imputation analyses for all secondary endpoints collected every 6 months over the 5-year study period, for purposes of efficiency the sensitivity analyses using multiple imputation (Proc MI in SAS) of missing values will be initially limited to the primary efficacy bone biopsy endpoints. After reviewing patterns of missing-ness in the secondary endpoints, additional sensitivity analyses involving multiple imputations may be performed at the request of the PI.

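### The primary biopsy model uses the baseline biopsy as both outcome and covariate: under compound symmetry its nominal 5% overall test rejects about 12-18% of the time under no effect, and the unstructured alternative has no maximum likelihood

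*SAP*

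**What the plan says.** SAP 7.4.1 applies one repeated-measures mixed model to each of the 8 primary endpoints. The endpoint is the dependent variable, and the other terms are "the baseline value of the bone biopsy endpoint and study cohort as covariates, biopsy time (baseline, 1 year, 2 year, and 4 year"). Time is the repeated measure and subject is random. A delay term adjusts the Cohort 2 baseline biopsy: "An indicator variable in the statistical model will set the effects of this time-dependent covariate to zero for Cohort 3 and for the post-baseline" rows of the Cohort 2 subjects. That term can act only if baseline biopsies are outcome rows. Nothing restricts the baseline covariate to post-baseline rows.

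On covariance, 7.4.1 states: "The repeated measures will be fit using both a compound symmetry and an unstructured covariance structure". The structure with the better Schwarz criterion is kept. Pairwise contrasts follow Fisher's protected LSD, with Bonferroni if the overall time effect is not significant. There is no correction across the 8 endpoints.

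SAP 7.4.2.3 uses the same form for the back-scattered imaging parameters: "the baseline value of the biopsy endpoint and study cohort as covariates, biopsy time (baseline, 1 year, 2 year, and 4 year"). SAP 7.4.2.4 does the same for the non-biopsy endpoints: "the baseline value of the non-biopsy endpoint, and study cohort as covariates, the experimental time-point as the repeated measure". The weaning model in 7.4.2.5 does not. It has subject effects "and repeated fixed effects for 3 study time-points within a subject", with baseline as one of the three time-points and no baseline covariate.

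**The concern.** Baseline can be a response in a longitudinal model or a covariate in a model of the on-treatment value. It cannot be both in a two-row model. A baseline row regressed on its own value carries no independent information, yet the fit counts it as data.

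This is the primary analysis of every primary endpoint, and the overall test opens the gate to the pairwise claims. An inflated gate passes its error on to statements that turnover differs between year 1 and later years. Whether the early rise in turnover persists is the question Protocol section 1 raises. The Cohort 3-only repeat required by SAP 4 inherits the problem with even fewer subjects.

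**Working it through.** **Inputs from the documents.** Two biopsies per subject (Protocol 4.5.6). In Cohort 3, "only 19 were actually enrolled and treated and of these, 8 subjects provided their on-treatment biopsy" (SAP 9). Cohort 2 comes from those eligible to "continue from among the 10 currently enrolled subjects will be enrolled in the other stratum" (Protocol 10.3), so at most 10. N with both biopsies is therefore 8 (Cohort 3 alone) to 8 + 10 = 18. Tests are two-sided at 0.05.

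**Assumptions.** Year splits; baseline/on-treatment correlation ρ of 0.2-0.8; on-treatment to baseline SD ratio of 1-2; Cohort 2 numbers of 0 of 8, 5 of 13 and 10 of 18; delays uniform over 1-4 years with no true effect; normality; within-subject df.

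**The plan's own figure.** Protocol 10.2 gives 93% power for a paired t-test with 8 per arm, change 10, SD 7. Noncentrality is 10×√8/7 = 4.04 on 7 df, giving 93.1%, so it reproduces. The SAP gives no operating characteristics for the mixed model that replaces it.

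**Why compound symmetry fails.** Let b be baseline and Y the on-treatment value, each with variance 1. Write D = Y − b and S = Y + b. The covariate has the same coefficient on both rows, so it cancels from D and adjusts only S. Compound symmetry treats D and the adjusted S as independent. In fact:

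- Var(D) = 2(1−ρ).
- Var(S given b) = 1−ρ², which is just the variance of the residual r of Y on b.
- Cov(D, adjusted S) = Var(r) = 1−ρ². Their correlation is √((1+ρ)/2), or 0.87 at ρ = 0.5. The model assumes 0.

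The implied subject variance is [(1−ρ²) − 2(1−ρ)]/4 = −(1−ρ)²/4, which is negative. A fit bounded at zero therefore tends to sit on the boundary.

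For year versus year, the model combines D and S by inverse variance. The ratio of true to claimed variance is 1 + 2(1−ρ²)/[2(1−ρ) + (1−ρ²)] = 1 + 2(1+ρ)/(3+ρ).

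| ρ | variance ratio | 1.96/√ratio | actual two-sided level |
|---|---|---|---|
| 0.2 | 1.75 | 1.48 | 13.8% |
| 0.5 | 1.86 | 1.44 | 15.0% |
| 0.8 | 1.95 | 1.40 | 16.0% |

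Year versus baseline is less affected, because S does not inform that contrast directly.

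**Small-sample simulation.** REML, covariance free to be negative, 4000 replicates per scenario (Monte Carlo SE about 0.5 points), no true differences:

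| Test at nominal 5% | Years separate (3/3/2, 6/4/3, 8/6/4) | Years 2 and 4 pooled (4/4, 6/7, 8/10) |
|---|---|---|
| Overall | 13.6-17.5% | 9.4-12.6% |
| Year v year (1 v 2 if separate) | 14.1-17.0% | 12.8-16.9% |
| Year v baseline | 6.3-12.1% | 5.6-8.5% |
| Any false pairwise claim under the SAP's gate | about 14-18% | about 9-13% |

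Holding the subject variance at or above zero changes little: with years separate, 13.0-17.4%, 12.9-16.9% and 6.7-11.9% for the first three rows. A wider grid (N = 8-24, ρ = 0-0.9, equal SDs) gives 11.8-17.2% overall, and 15-24% if residual df are used.

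**Isolating the cause.** Removing only the baseline covariate, with equal SDs, brings the overall test to 4.9-6.6%. The double use is therefore the cause, not the small sample.

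**Unstructured covariance.** Set the baseline slope to 1 and the other baseline-row terms to 0. Every baseline residual is then exactly zero, and as the baseline variance tends to 0 the likelihood grows without limit. At slopes 0.5, 0.99 and 0.99999, −2 log L is 37, −64, −244 (N = 13) and 59, −81, −330 (N = 18). REML behaves the same way: 19.6 falling to −185.9 as the baseline variance goes from 1 to 1e-8 (N = 15). In addition, no subject has two on-treatment biopsies, so covariances among years 1, 2 and 4 have no data.

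**SAP 7.4.2.4.** With four complete time-points the compound-symmetry tests hold their level (4.3-4.7%, 19 or 29 subjects). The slope-of-1 degeneracy remains.

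**The case against.** **The sizes rest on unknowns.** Cohort 2 pairs, year splits, correlation and SD ratio are not in the documents. At equal SDs one set of runs gave 11.8-15.2% overall, and 17.1% was reached only with the on-treatment SD doubled. Another equal-SD grid did reach 17.2% at high correlation. The exact figure is uncertain; the direction is not.

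**Change from baseline is less affected.** This is correct. With years pooled and covariance unrestricted, some contrasts are near 5% (4.1-10.0% in one grid), so inflation of that contrast is not established in every configuration.

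**The global null is unrealistic for some endpoints.** The pilot change in mineralizing perimeter was 22 (SD 7)%. With a 3-SD shift the overall test rejects every time under either model, so the gate is irrelevant. Year versus year was still 13.4% against 5.1% without the covariate.

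**7.4.2.3 names no covariance structure.** True; compound-symmetry inflation there is inferred from 7.4.1.

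**7.4.2.4 will not have complete data.** True, and this widens the problem. With assumed missing visits (20% at month 6, 40% at later points), rates of roughly 7-9% were found.

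**Dropping the covariate is enough.** It is at equal SDs. If the on-treatment SD is 2-3 times baseline, compound symmetry without the covariate still ran at 9-14% overall. Log-transformation may reduce that but cannot be relied on in advance.

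**The safeguards would catch it.** Non-convergence might expose the unstructured failure. The residual checks in 7.4.1 are discretionary and do not correct a prespecified compound-symmetry fit.

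**Conclusion.** The primary model is wrong as written. With the covariate on both rows and two biopsies per subject, the nominal 5% overall test runs at about 12-18% with years separate and about 9-13% with years 2 and 4 pooled. Year-versus-year contrasts run at about 12-17%. Year versus baseline runs from near nominal up to about 12%. These are null rejection rates under the assumptions listed, with within-subject df. They matter most for endpoints with small true change and for year-versus-year claims. The unbounded unstructured likelihood needs none of those assumptions: one of the two candidate structures cannot be fitted, so the selection rule is undefined.

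**What to change.** - **7.4.1 and 7.4.2.3:** keep the baseline biopsy as a response and delete the baseline-value covariate. Keep cohort and, in 7.4.1, the Cohort 2 delay term.
- **Covariance:** prespecify one 2x2 unstructured matrix (pre-treatment, on-treatment) with Kenward-Roger df. Delete the compound-symmetry versus unstructured selection for the biopsy models. In simulation (3000 replicates) this runs at 4.8-5.6% (N = 18), 5.4-6.2% (N = 13) and 5.3-7.9% (N = 8).
- **Companion analysis:** because that model is still somewhat liberal at N = 8, also report the regression of on-treatment minus baseline on biopsy year plus the Cohort 2 delay. This is the change-from-baseline analysis of Protocol 10.1 with the delay added. It gives both types of contrast and runs at 4.5-5.4% at every N.
- **ANCOVA** of the on-treatment value on baseline should be supplementary and for year versus year only. It gives no direct year-versus-baseline contrast and loses the delay adjustment.
- **7.4.2.4:** drop the baseline covariate so that the unstructured option is defined.

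The cost is SAP wording and a changed model call, with no new data. P-values will tend to be less favourable.

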846 either surrogate biomarkers for bone histomorphometric measures or as classifiers that could be used to
847 identify subjects more responsive to HPTH treatment.

848 Subjects and their data will be monitored closely throughout the study for safety; data will be submitted
849 regularly for DSMC review as described in Section 15. In addition, preliminary analyses using methods
850 described above may be performed when all evaluable subjects meet certain early milestones, for
851 example, after all subjects have completed their one year biopsy. These analyses will be designed to
852 evaluate early changes from baseline in primary and secondary measures after one year of HPTH
853 treatment and to assess the predictive values of selected secondary measures in relation to the primary
854 endpoints.

855 **10.2 Power Analysis**

856 Sample size calculations were based on 2 of the primary bone biopsy outcome measures, cancellous bone
857 mineralizing perimeter and bone formation rate, using preliminary data from the 5 previously enrolled
858 subjects who had biopsies at baseline and at 1 year of HPTH therapy. For mineralizing perimeter, the
859 mean (standard deviation) of the 1-year changes from baseline was 22 (7) %, and for bone formation rate
860 it was 0.23 (0.07) $\mu\text{m}^2/\text{mm}/\text{d}$. For design purposes, we assumed that a clinically meaningful change in
861 mineralizing perimeter from baseline to either 1, 2 or 4 years of therapy is 10% and will establish the
862 sample size required to detect a difference at least that large with adequate power. Using a two-tailed 0.05
863 level paired t-test, we found that 8 new subjects in each follow-up arm yielded 93% power to detect a
864 difference of 10% at any of the follow-up times. For bone formation rate, we assumed that a clinically
865 meaningful change from baseline is 0.10 $\mu\text{m}^2/\text{mm}/\text{d}$, which corresponds to an identical standardized
866 minimum detectable effect size of $0.10/0.07=1.4$ compared to $10/7=1.4$ for mineralizing perimeter. As a
867 result, 8 new subjects per arm will also yield 93% power to detect significant paired differences in bone
868 formation rate of 0.10 $\mu\text{m}^2/\text{mm}/\text{d}$.

869 A secondary analysis objective of the primary bone biopsy endpoints is to determine if there are
870 differences between the changes from baseline over time, using analysis of variance (ANOVA) for these

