10. LIST OF PLANNED TABLES

Subject listings associated with the tables below will be provided. Experimental time refers to the baseline, last hPTH treatment, and post-hPTH follow-up visits. Additional tables (eg, those based on the results of sensitivity analysis) will be provided. Other displays, as requested by the PI may be provided as well.

Table Type	Table
Disposition	Summary of Subject Disposition
Demographics	Summary of Study Enrollment by Demographic Characteristics
hPTH Therapy	Summary of the Duration of hPTH Therapy
Primary Efficacy	Summary Statistics of Primary Bone Biopsy Endpoints by Biopsy Year. (Separate tables for Cohorts 2, 3, and Cohort 2 combined with Cohort 3)
	Repeated Measures Analysis of Primary Efficacy Analysis (Separate tables for Cohorts 2, 3, and Cohort 2 combined with Cohort 3)
Secondary Efficacy	Summary of Bone Mineralization Density Assessed by Back-Scattered Electron Imaging by Years of hPTH therapy
	Summary of Biochemical Markers of Bone Metabolism by Experimental Time Including the Statistical Significance of Changes.
	Summary of Blood and Urine Chemistries by Experimental Time Including the Statistical Significance of Changes.
	Summary of Bone Mineralization Density Assessed by DXA and Quantitative CT by Experimental Time Including the Statistical Significance of Changes.
	Summary of Nephrocalcinosis and Nephrolithiasis by Time on Study Drug
	Summary of Fatigue Symptom Inventory and 6-Minute Walk Test by Experimental Time Including the Statistical Significance of Changes.
	Summary of SF-36 Health Survey by Experimental Time Including the Statistical Significance of Changes.
Adverse Events (as provided to DSMB)	Summary of Adverse Events Occurring While on hPTH 1-34 or After Withdrawal from hPTH 1-34
	Summary of Adverse Events Occurring on or after hPTH 1-34
	Summary of Adverse Events Occurring While on Conventional Care
	Summary of Adverse Events for Subjects on Conventional Care
	Summary of Adverse Events Occurring While on hPTH 1-34 or After Withdrawal from hPTH 1-34: Current PI
	Summary of Adverse Events Occurring While on hPTH 1-34 or After Withdrawal from hPTH 1-34: Prior to Current PI
	Summary of Adverse Events Occurring While on Conventional Care: Current PI
	Summary of Adverse Events Occurring While on Conventional Care: Prior to Current PI

	Summary of Adverse Events Occurring While on hPTH 1-34 or After Withdrawal from hPTH 1-34; Related (Unlikely, Possible, Probable, or Definite) to hPTH 1-34

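### SAP 7.4.1 lets the observed sign of the 4-year effect decide whether year 4 is pooled with year 2 or dropped from the primary model

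*SAP*

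**What the plan says.** The primary model in SAP 7.4.1 has biopsy time as a four-level factor: baseline, 1, 2 and 4 years. The same section then allows two departures:

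- Years 2 and 4 "may be combined into one group provided their effects are qualitatively similar (i.e. the estimates of their effects are in the same direction".
- When the two disagree qualitatively, "then the 4-year biopsies may be dropped from the analysis due to its small sample size".

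Pairwise comparisons are adjusted "using Fisher's protected LSD with Bonferroni corrections when the overall effect of biopsy year is not statistically significant".

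SAP 7.4.2.3, on the back-scattered electron imaging parameters, has a different pooling test. There the two years "may be collapsed into one biopsy group for analysis purposes if the 2 and 4 year biopsies appear to have similar effect sizes and variances", and if they differ "the 4-year biopsy endpoints may be dropped from the analysis due to their small sample sizes".

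SAP 9 says "We will evaluate the possibility of combining the 2- and 4- year biopsy groups to address this issue" and refers to 7.4.1 for details.

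SAP 10 still plans "Summary Statistics of Primary Bone Biopsy Endpoints by Biopsy Year", so the 4-year data stay visible descriptively.

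**The concern.** Sample size is the stated reason for both departures, but sample size does not decide between them. With three 4-year biopsies, year 4 is retained if its estimate has the same sign as year 2 and may be removed if it has the opposite sign. Magnitude plays no part, so a 4-year effect near zero is pooled or dropped largely by chance.

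Both branches say *may*, so keeping the years separate is also allowed and the choice can be made after the results are seen. The SAP does not say whether an effect is measured from baseline or from year 1. It also does not say whether one decision covers all eight primary endpoints.

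The protocol's primary objective (2.1) is change at 1, 2 and 4 years. Its introduction says it is unknown whether the first-year rise in bone volume and remodeling lasts or fades. The rule acts on the result that answers this. A 4-year reversal is usually removed from the inferential result, and attenuation is averaged into a single late figure.

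**Working it through.** **Inputs from the documents.** Mineralizing perimeter: pilot 1-year change +22 with SD 7, meaningful change 10, planning example +10/+15/+21 (Protocol 10.2); larger SD of 15 (Protocol 10.1). Two-sided alpha 0.05 (Protocol 10.1).

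**Assumptions.** An effect is change from baseline. The rule is always applied. The 2-/4-year sample sizes are 4/3, with 3/2, 5/4, 3/1 and 5/1 as the range. True late effects are as listed below.

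**The plan's own figures.** The noncentral-t power of a paired t-test with n = 8, change 10 and SD 7 is 93.1% (stated: 93%). The ANOVA example (+10/+15/+21, 8 per arm) gives 74.8% (stated: 75%). The planning inputs are therefore read correctly.

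**Step 1: how often year 4 is dropped.** With s = SD/√n for each arm:

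P(pool) = Φ(μ2/s2)·Φ(μ4/s4) + Φ(−μ2/s2)·Φ(−μ4/s4)

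For 4/3 and SD 7, s2 = 7/√4 = 3.50 and s4 = 7/√3 = 4.04. For true +10/−5:

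P(pool) = Φ(2.86)·Φ(−1.24) + Φ(−2.86)·Φ(1.24) = 0.998×0.108 + 0.002×0.892 = 0.11, so year 4 is dropped in 89%.

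A simulation with 1,000,000 replicates per scenario gives the same.

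**Step 2: the reported late change.** Unconditional pooling averages (4μ2 + 3μ4)/7.

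| True change, year 2 / year 4 | Year 4 dropped | Late estimate under the rule | Unconditional pooling |
|---|---|---|---|
| +22 / 0 | 50% | +18.0 | 88/7 = +12.6 |
| +22 / +2 | 31% | +14.3 when pooled | 94/7 = +13.4 |
| +10 / −5 | 89% | +9.6 | 25/7 = +3.6 |
| +15 / +21 | under 0.2% | +17.6 | 123/7 = +17.6 |

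- First row: when pooled, year 4 averages 4.04×0.798 = 3.22, so the pooled value is (88 + 9.67)/7 = 13.95. Averaged equally with 22 (year 2 alone), this gives 18.0.
- Over the other arm sizes, +10/−5 is dropped in 76-92% (60-71% at SD 15), and +22/+2 is pooled in 61-72%.
- In the last row, based on the protocol's own example, there is no selection bias, although the difference between the years is merged.

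**Step 3: type I error of late versus baseline.** This used 200,000 replicates with estimated common variance. The SAP's gate was modelled as 0.05 if the overall F-test is significant, otherwise 0.05/3. The 1/2/4-year sizes were 6/4/3, 6/3/2, 8/5/4, 5/3/1 and 4/5/4. Both late effects are truly zero.

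| Year-1 effect | Sign rule | Unconditional pooling |
|---|---|---|
| Real (+10 or +22) | 7.1-7.4% | 4.8-5.0% |
| None | 4.0-4.2% | 2.6-2.8% |

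With no effect at any time, the overall test under the rule rejects in 6.7%. A separate simulation without the gate, using partly different arm sizes, gave 7.3-7.5% against 4.9-5.0%.

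**The case against.** Several points on the other side are fair.

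- **Section 9 adds no discretion of its own.** It defers to 7.4.1. This stands; the discretion comes from *may* in 7.4.1, and that is enough.
- **The ambiguities have natural readings.** Separate analyses per endpoint suggest a decision per endpoint, and the endpoints are defined as changes under therapy. The calculations use change from baseline. A per-endpoint decision, however, means the eight endpoints could end with different groupings.
- **A fall below baseline is implausible for turnover indices that start low.** This is reasonable for the six remodeling endpoints, and +22/0 is then the closer match to the protocol's question. The rule still drops year 4 half the time there. For cancellous bone volume and cortical porosity number, the documents give no SD.
- **The inflation is modest and conditional.** This is correct. Most masking of attenuation also comes from pooling itself: for +22/+2, selection adds only 14.3 − 13.4 = 0.9.
- **The scale differs.** The SAP uses z-scores where norms exist, in a mixed model with cohort and time-delay covariates. The figures show direction and rough size only.
- **Outcome-dependent pooling was already in Protocol 10.1.** That rule followed a non-significant ANOVA, pooled all three times and had no option to drop year 4.
- **A separate 4-year level is hard to support.** SAP 9 reports 8 on-treatment biopsies among new subjects, and Protocol 10.3 puts the earlier conventional-care pool at no more than 10, so at most 18 in total. A separate 4-year variance would be barely estimable, or not at all with one biopsy. But the SAP's default model already has this difficulty, and its compound-symmetry option implies a common variance.
- **The 7.4.2.3 criterion is not sign-based, and those analyses are called exploratory.** True, and no size was calculated for them. The criterion still depends on the outcome and carries the same drop option.

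None of this removes the defect. The authors knew the numbers were small, so the grouping could have been set on sample size alone.

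**Conclusion.** The concern holds. The primary model's late estimate can be selected on the observed direction of the outcome, at the analyst's option. The effect is large when the true 4-year change is near zero or reversed: year 4 is lost in 50% of trials for +22/0 and 89% for +10/−5. It is negligible when both late effects are clearly in the same direction. Type I error for the late contrast is about 7% rather than 5%, but only when year 1 has a real effect and both late effects are zero.

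These sizes rest on assumed arm sizes, the mineralizing-perimeter SD, a simplified change-score model and the rule always being applied. That the trigger is the outcome rests on the SAP text alone. What is at risk is the model-based 4-year estimate, interval and test, not every display of the 4-year data. It should be fixed before the primary analysis is run.

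**What to change.** - Delete the direction-based pooling rule and the drop option from SAP 7.4.1, and the pooling and drop options from 7.4.2.3. Align section 9.
- Keep 1, 2 and 4 years as separate model levels for every endpoint, and report the 4-year model estimate with its confidence interval.
- If a more precise late estimate is wanted, prespecify one pooled 2-and-4-year contrast for all endpoints, regardless of observed direction, shown beside the separate estimates.

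The cost is SAP wording and a wide 4-year interval. With SD 7 and a common variance, the half-width is t(0.975, N−3) × 7/√n4, where N is the number of subjects over the three arms:

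| 1/2/4-year n | Half-width |
|---|---|
| 8/5/4 | 2.145 × 3.50 = ±7.5 |
| 6/4/3 | 2.228 × 4.04 = ±9.0 |
| 6/3/2 | 2.306 × 4.95 = ±11.4 |
| 5/3/1 | 2.447 × 7.00 = ±17.1 |

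A wide interval reports the uncertainty as it is; removal conditional on sign hides it.
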